1.3.3 Correlative Studies Background

Correlative science to inform optimal use of pembrolizumab + vactosertib with chemotherapy in patients with metastatic CRC and to identify candidate biomarkers of response, resistance or toxicity, is an integral part of this study. As a result, serial blood samples as well as tissues from biopsies and surgical resection will be used to perform deep immunologic and molecular profiling prior to, during and following treatment.

Correlative research will be performed on:

- Baseline liver tumor biopsies (just prior to administration of neoadjuvant treatment).
- Surgical resection specimens (after neoadjuvant pembrolizumab-based treatment). Note that if patients undergo resection of multiple liver metastases, surgical removal of liver metastases plus colon primary, or other cases where surgical specimens are available from multiple sites, collection of multiple specimens is encouraged, with priority given to the liver metastasis corresponding to the pre-treatment biopsy.
- If a patient is unable to undergo surgery but had a pre-treatment biopsy that was confirmed to contain adequate tumor material for analysis and received one cycle of neoadjuvant pembrolizumab-based treatment, a second liver biopsy should be performed after the cycle of neoadjuvant treatment (biopsy of same liver metastasis as sampled in the pre-treatment biopsy preferred).
- Serial blood samples (pre-neoadjuvant treatment, pre-surgery, post-surgery, and at progression or end of study, whichever comes first).
- Stool samples collected at screening (-4 and -2 days of first pembrolizumab dose), at pre-surgical evaluation, and at the safety follow-up visit [optional].

Goals of the correlative research are to determine how immunotherapy perturbs both the circulating and intratumoral immune responses. Assays will be detailed in the Procedure Manual.

Stool will be collected, and a stool questionnaire will be completed at screening (-4 and -2 days of first pembrolizumab dose), at pre-surgical evaluation, and at the safety follow-up visit [optional] to assess the microbiome associated with clinical activity. This research may help identify factors predictive of pembrolizumab-based treatment response and resistance and novel targets for cancer immunotherapy.

Additionally, a dietary and physical activity questionnaire will be administered at screening (-28 to -1 day prior to first pembrolizumab dose).

1.3.4 Correlative Studies Hypotheses

Translational research hypotheses to be investigated are:

- a) Pembrolizumab-based treatment will induce increased populations of TILs within metastatic CRC tumor samples.
- b) Increase in TILs induced by pembrolizumab-based treatment is correlated with pathological response in patients with metastatic CRC.
- c) Pembrolizumab-based treatment will increase PD-L1 expression in TICCs and may be associated with pathological response.
- d) Distinct T cell repertoire changes in tumor tissue will be associated with response, resistance, or toxicity to pembrolizumab-based treatment.
- e) Pembrolizumab-based treatment will induce characteristic changes in circulating T cell populations.

Phase 2, Pembrolizumab, Vactosertib

- f) Distinct T cell repertoires in tumor tissue as well as in circulating T cells may be associated with response/resistance or toxicity to pembrolizumab-based treatment, and may in turn serve as biomarkers of response/resistance or toxicity.
- g) Molecular characteristics beyond MSI/MMR (candidates include BRAF, BAP1, and SETD2) may be associated with higher levels of TILs or PD-L1 expression on TILs in response to pembrolizumab-based treatment, and thus be candidates for further study as predictive biomarkers in patients with metastatic CRC treated with immunotherapy.
- h) Genomic mutations and gene copy variants may associate with clinical and/or immunologic response to therapy.
- i) Correlate changes in microbiome composition and diversity (by metagenomic sequencing and untargeted metabolomics of stool collected before, during, and after immunotherapy), with diet and lifestyle factors.

1.3.5 Biomarker Research

Cancer immunotherapies represent an important and novel class of antitumor agents. However, the mechanism of action of these exciting new therapies is not completely understood and much remains to be learned regarding how best to leverage these new drugs in treating patients. Thus, to aid future patients, it is important to investigate the determinants of response or resistance to cancer immunotherapy and other treatments administered, as well as determinants of AEs in the course of our clinical trials. These efforts will identify novel predictive/pharmacodynamic biomarkers and generate information that will better guide single-agent and combination therapy with immuno-oncology (IO) drugs. To identify novel biomarkers, biospecimens (i.e., blood components, tumor material, and microbiome) will be collected to support analyses of cellular components (e.g., protein, DNA, RNA, metabolites) and other circulating molecules. Procedures are detailed in the Lab Manual. Investigations may include but are not limited to:

Tissue proteomic analysis by immunohistochemistry (IHC) and Immunofluorescence (IF)

IHC staining of PD-L1 protein in tumor sections has been shown to correlate with response to pembrolizumab in patients with NSCLC, and an *in vitro* diagnostic (IVD) device has been developed for use with pembrolizumab in NSCLC. Preliminary data indicates that this association may also be true in additional cancer types (i.e., triple negative breast, head and neck, and gastric cancer). Additional proteins expressing in the tumor microenvironment at baseline or following treatment may also correlate with response to pembrolizumab. Therefore, tumor tissue may be subjected to proteomic analyses using a variety of platforms that could include but are not limited to IHC and IF. Multiplex IHC and IF may be performed on tumor core samples and resected tissues utilizing immune marker panels to assess for different cell types, including T cells, antigen presenting cells and stromal cells. Stained sections will be scanned, and the number of stained cells enumerated per area of tissue by computerized image analysis. The staining panels to be utilized will be developed in collaboration and agreement with Merck and the Principal Investigator. This approach could identify novel protein biomarkers that could aid in patient selection for pembrolizumab (MK-3475) therapy.

For the Primary Endpoint, defined as the proportion of patient with a ≥ 2 -fold increase in TILs in post- vs. pre-pembrolizumab-based treatment tumor specimens, TILs will be enumerated per area of tissue (5 high power fields). We have developed this methodology and applied it to other *Phase 2, Pembrolizumab, Vactosertib*

neoadjuvant immunotherapy trials (28, 29). This automated methodology can be applied to biopsies and resection tissues.

Gene Expression Profile (GEP)

Intratumoral expression levels of select genes will be analyzed using an analytically validated platform, such as the NanoString nCounter Analysis System and RNAseq. Association between the immune-related GEP and response to pembrolizumab has been established using these genes in melanoma and in cancers from clinical studies KN012 (head and neck, bladder, and gastric cancers) and KN028 (ovarian, esophageal, and other cancers). Data from these cohorts has been used to derive a GEP, which combines the expression levels of several key genes into a single scalar score. The GEP includes genes from immune-regulatory pathways and a GEP score will be tested for association with response to pembrolizumab-based treatment in retrospective fashion.

Flow Cytometry

Peripheral blood mononuclear cells (PBMC) and dissociated single cell suspensions of fresh tissue (where available) will be assessed for immune cell composition and functional status using flow cytometry staining. Other cell types (including stroma and tumor cells) may also be assessed by flow cytometry.

Additional biomarker research to identify factors important for pembrolizumab-based treatment therapy may also be pursued. For example, tumor and blood samples (including serum and plasma) from this study may undergo proteomic, genomic, metabolomic, and transcriptional analyses. Additional research may evaluate factors important for predicting responsiveness or resistance to pembrolizumab-based treatment and other immunologic targets.

Germline (blood) genetic analyses (e.g. single-nucleotide polymorphism [SNP] analyses, whole exome sequencing, whole genome sequencing)

This research will also evaluate whether genetic variation within a clinical trial population correlates with response to the treatment(s) under evaluation. If genetic variation is found to correlate with efficacy or AEs, the data might inform hypotheses regarding optimal use of therapies in the patient population. Furthermore, it is important to evaluate germline DNA variation across the genome in order to interpret tumor-specific DNA mutations. Finally, MSI may be evaluated as this is an important biomarker for some cancers (i.e. CRC).

Other blood-derived biomarkers- Proteomic Analysis

In addition to expression on the tumor tissue, PD-L1 can be shed from tumor and released into the blood. Assays such as enzyme-linked immunoassay (ELISA) can measure PD-L1 in serum. Correlation of expression with response to pembrolizumab (MK-3475) therapy may identify new approaches for predictive biomarkers in blood, representing a major advance from today's reliance on assessing tumor biomarkers. This research would serve to develop such assays for future clinical use.

Genetic (DNA) analyses from tumor

The application of new technologies, such as next generation sequencing, has provided scientists the opportunity to identify tumor-specific DNA changes (i.e. mutations, methylation status, MSI). Key molecular changes of interest to immune-oncology drug development include the mutational burden of tumors and the clonality of T cells in the tumor microenvironment. Increased mutational burden (sometimes referred to as a "hyper-mutated" state) may generate neo-antigen presentation in the tumor microenvironment. To conduct this type of research, it is important to identify tumor-specific mutations that occur across all genes in the tumor genome. Thus, genome-wide approaches may be used for this effort. Note that in order to understand tumor-specific mutations; it is necessary to compare the tumor genome with the germline genome.

Tumor and blood RNA analyses

Both genome-wide and targeted messenger RNA (mRNA) expression profiling and sequencing in tumor tissue and in blood may be performed to define gene signatures that correlate to clinical response to pembrolizumab-based treatment or other immunotherapies. Pembrolizumab induces a response in tumors that likely reflects an inflamed/immune phenotype. Specific immune-related gene sets (i.e. those capturing interferon-gamma transcriptional pathways) may be evaluated and new signatures may be identified. Individual genes related to the immune system may also be evaluated (e.g. IL-10). MicroRNA profiling may also be pursued.

Planned Genetic Analysis

Genetic variation may impact a patient's response to therapy, susceptibility to, and severity and progression of disease. Variable response to therapy may be due to genetic determinants that impact drug absorption, distribution, metabolism, and excretion; mechanism of action of the drug; disease etiology; and/or molecular subtype of the disease being treated. Therefore, where local regulations and Institutional Review Boards (IRBs)/Ethics Review Committees (ERCs) allow, a sample will be collected for DNA analysis from consenting patients.

DNA samples will be used for research related to the study treatment(s), the disease under study and related diseases. They may also be used to develop tests/assays including diagnostic tests related to the disease under study, related diseases and study drug(s). Genetic research may consist of the analysis of 1 or more candidate genes or the analysis of genetic markers throughout the genome (or analysis of the entire genome, as appropriate).

DNA samples will be analyzed for variation across the entire genome. Analyses may be conducted if it is hypothesized that this may help further understand the clinical data.

The samples may be analyzed as part of a multi-study assessment of genetic factors involved in the response to understand study disease or related conditions.

Whole Exome Sequencing

Flash freezing of fresh biopsy cores in liquid nitrogen may allow for RNA-sequencing and Whole Exome Sequencing of tumor. This analysis will be performed using fresh frozen tissue specimens from both core needle biopsy (CNB) and resected tumor tissues.

Microbiome analysis of stool

Stool samples from this study will be collected for analyses including, but not limited to, metagenomic sequencing and untargeted metabolomics to reveal changes in gut microbial structure and function during treatment, including overall diversity and relative abundance of gut bacterial species, genes, and metabolites implicated in response to immunotherapy.

1.3.6 Future Biomedical Research Sample Collection

The investigators will conduct Future Biomedical Research on specimens for which consent was provided during this clinical trial. This research may include flow cytometry, genetic analyses (DNA), gene expression profiling (RNA), proteomics, metabolomics (serum, plasma), microbiome analysis of stool, characterization of circulating cell free DNA, and/or the measurement of other analytes, depending on which specimens are consented for future biomedical research.

Such research is for biomarker testing to address emergent questions not described elsewhere in the protocol and will only be conducted on specimens from appropriately consented participants. The objective of collecting/retaining specimens for Future Biomedical Research is to explore and identify biomarkers that inform the scientific understanding of diseases and/or their therapeutic treatments. The overarching goal is to use such information to develop safer, more effective drugs/vaccines, and/or to ensure that participants receive the correct dose of the correct drug/vaccine at the correct time. Decisions on Future Biomedical Research will be made by the Joint Steering Committee.

1.3.6.1 Future Biomedical Research Samples

The following specimens could be obtained as part of Future Biomedical Research:

- DNA for future research
- Leftover tumor for future research
- Leftover DNA and RNA from Correlative Studies
- Leftover plasma and serum from Biomarker Studies
- Leftover PBMC from whole blood from Correlative Studies
- Microbiome

2 Objectives of the Study

2.1 Hypothesis

We hypothesize that pembrolizumab plus vactosertib will increase tumor-infiltrating immune cells (TICCs) and promote response without increasing perioperative complications.

2.2 Primary Objective and Endpoint

Primary Objective	Endpoint	Time Frame
To characterize the change in the populations of TILs induced by	The primary endpoint is the proportion of patients with a ≥ 2 -fold increase in the	From pre-treatment to surgery.

Phase 2, Pembrolizumab, Vactosertib

Primary Objective	Endpoint	Time Frame
neoadjuvant pembrolizumab plus vactosertib in patients with metastatic CRC.	TILs per unit area (5 high power fields) in post- vs. pre-pembrolizumab-based treatment tumor specimens.	

2.3 Secondary Objectives and Endpoints

Secondary Objectives	Endpoints	Time Frame
1. To establish the safety/toxicity profile of pembrolizumab-based treatment in the perioperative setting for patients with CRC with resectable hepatic metastases.	
 Proportion of participants with Adverse Events, as graded by NCI CTCAE version 5.0 Proportion of participants with events of clinical interest (ECIs) Rates of perioperative complications 	From initiation of study treatment until 1 year post last dose of pembrolizumab.
2. To explore the efficacy of pembrolizumab plus vactosertib in patients with CRC with resectable hepatic metastases.	
 R0 resection rate Pathologic response in resected tumor Objective response rate 2-year relapse-free survival (RFS) 	From baseline to surgery. From surgery to up to 2 years post-surgery.

2.4 Exploratory Objectives and Endpoints

Exploratory Objectives	Endpoints

 To determine the impact of pembrolizumab-based treatment on PD L1 expression in tumor cells and TIICs, in patients with mCRC. To determine the change in T cell repertoire within the tumor and blood induced by neoadjuvant pembrolizumab-based treatment in patients with mCRC. To explore molecular profiles to identify potentially predictive biomarkers for patients with metastatic CRC treated with immunotherapy (including but not limited to MSI testing). To correlate change in TIICs, PDL-1 expression, and T cell repertoires as well as molecular profiles with response/resistance and toxicity. To identify immune response mRNA expression analysis to derive signatures associated with tumor response 	
 Change in T-cell repertoire in pre-neoadjuvant treatment liver biopsies vs. surgical tumor specimens as well as in blood samples from the same time-points Change in PD-L1 expression and other molecular markers in pre-neoadjuvant treatment liver biopsies vs. surgical tumor specimens Correlate changes in microbiome composition and diversity (by metagenomic sequencing and untargeted metabolomics of stool collected before, during, and after immunotherapy), with diet and lifestyle factors determined by self-reported questionnaires. Explore the correlation between change in TILs and T-cell repertoire.

Exploratory Objectives	Endpoints

 6. To identify genomic mutations and gene copy aberrations associated with response and resistance to therapy 7. To correlate changes in microbiome composition and diversity with diet and lifestyle factors 	

3 Study Design

3.1 Characteristics

This is a single arm, open-label trial evaluating the feasibility, immune effects, safety, and efficacy of pembrolizumab-based treatment in the preoperative setting for patients with CRC undergoing planned liver resection for hepatic metastases. The primary endpoint is the proportion of patients with a ≥ 2 -fold increase in the number of TILs in post- vs. pre-pembrolizumab-based treatment tumor specimens.

Based on the results of this initial cohort, this trial may be subsequently amended to explore other novel pembrolizumab-based combinations (such as pembrolizumab in combination with another IO agent, chemotherapeutic, or a molecularly targeted agent that potentiates the efficacy of pembrolizumab) that will be decided by the Joint Steering Committee (JSC). Each of these new cohorts will be tested and enrolled to in sequential, non-randomized fashion. The trial is not designed to compare arms.

3.2 Number of Patients

In order to accrue 17 patients who are evaluable for the primary endpoint, the plan is to enroll a total of 19 patients. If 2 or more of first 6 patients are unable to undergo planned surgical resection of their liver metastases in timely fashion (i.e., within 4-6 weeks of the final chemotherapy administration [if applicable]) or experience surgical complications attributed to pembrolizumab-based treatment, accrual will be suspended, and our strategy will be revisited.

3.3 Eligibility Criteria

Patients must have baseline evaluations performed prior to dosing of study drug and must meet all of the inclusion and none of the exclusion criteria. In addition, the patient must be thoroughly informed about all aspects of the study, including the study visit schedule and required evaluations and all regulatory requirements for informed consent. The written informed consent form (ICF) must be obtained from the patient prior to enrollment. The following criteria apply to all patients enrolled onto the study unless otherwise specified.

3.3.1 Inclusion Criteria

Patients are eligible for this trial if all of the following inclusion criteria are met:

1. Has histologically or cytologically confirmed CRC with liver metastases. In addition to liver metastases, extrahepatic metastases (e.g. pulmonary metastases) may be permitted if all

other eligibility criteria are met. Patients are permitted to have primary tumor *in situ* (Neoadjuvant Arm only).

2. Has received previous oxaliplatin-based chemotherapy.
 - a. FOLFOX or CapeOx does not need to be a direct lead-in to this study.
 - b. If chemotherapy is a direct lead-in to this study, concurrent mAb therapy (bevacizumab, cetuximab, or panitumumab) is acceptable, however the antibody must be omitted from the final cycle of chemotherapy prior to pembrolizumab.
3. Is an appropriate candidate to undergo liver biopsy and resection (\pm ablation) of liver metastases (Neoadjuvant Arm Only)
4. Is willing and able to provide written informed consent/assent for the trial. The patient may also provide consent for Future Biomedical Research. However, the patient may participate in the main trial without participating in Future Biomedical Research.
5. Is ≥ 18 years of age on day of signing informed consent.
6. Has measurable disease based on RECIST 1.1 as assessed by the investigator. Lesions situated in a previously irradiated area are considered measurable if progression has been demonstrated in such lesions. (Neoadjuvant Arm Only)
7. Is willing to provide tissue from a newly obtained core or excisional biopsy of a tumor lesion. Newly-obtained is defined as a specimen obtained after last dose of standard of care lead-in chemotherapy [if applicable] and within 28 days prior to first dose of pembrolizumab. (Neoadjuvant Arm Only)
8. Has a performance status of 0 or 1 on the Eastern Cooperative Oncology Group (ECOG) Performance Scale (Appendix 1).
9. Has adequate organ function as defined in Table 1, within 10 days of treatment initiation.

Table 1 Adequate Organ Function Laboratory Values

System	Laboratory Value
Hematological	
Absolute neutrophil count (ANC)	$\geq 1,500/\mu\text{L}$
Platelets	$\geq 100,000/\mu\text{L}$
Hemoglobin	$\geq 9 \text{ g/dL}$ or $\geq 5.6 \text{ mmol/L}$ without transfusion or erythropoietin (EPO) dependency (within 7 days of assessment)
Renal	
Serum creatinine OR Measured or calculated ^a creatinine clearance (GFR can also be used in place of creatinine or CrCl)	$\leq 1.5 \times$ upper limit of normal (ULN) OR $\geq 60 \text{ mL/min}$ for patient with creatinine levels $> 1.5 \times$ institutional ULN
Hepatic	
Serum total bilirubin	$\leq 1.5 \times$ ULN OR Direct bilirubin \leq ULN for patients with total bilirubin levels > 1.5 ULN
AST (SGOT) and ALT (SGPT)	$\leq 2.5 \times$ ULN
Albumin	$> 2.5 \text{ mg/dL}$

Phase 2, Pembrolizumab, Vactosertib

System	Laboratory Value
Coagulation	
International Normalized Ratio (INR) or Prothrombin Time (PT)	$\leq 1.5 \times \text{ULN}$ unless patient is receiving anticoagulant therapy as long as PT or PTT is within therapeutic range of intended use of anticoagulants
Activated Partial Thromboplastin Time (aPTT)	$\leq 1.5 \times \text{ULN}$ unless patient is receiving anticoagulant therapy as long as PT or PTT is within therapeutic range of intended use of anticoagulants
^a Creatinine clearance should be calculated per institutional standard.	

10. Female patients of childbearing potential must have a negative urine or serum pregnancy test within 72 hours prior to receiving the first dose of study medication (Day 1). If the urine test is positive or cannot be confirmed as negative, a serum pregnancy test will be required.
11. Female patients of childbearing potential must be willing to use an adequate method of contraception* as outlined in Section 6.6, for the course of the study through 120 days after the last dose of study medication.
12. Male patients of childbearing potential must agree to use an adequate method of contraception* as outlined in Section 6.6, starting with the first dose of study therapy through 120 days after the last dose of study therapy.

*Note: Abstinence is acceptable if this is the usual lifestyle and preferred contraception for the patient.

13. Have locally confirmed MSS or pMMR CRC. MSS is defined as 0-1 allelic shifts among 3-5 tumor microsatellite loci using a PCR-based assay. pMMR is defined as presence of protein expression of 4 MMR enzymes (MLH1, MSH2, MSH6 and PMS2) by immunohistochemistry.
14. Have no radiographic evidence of malignancy as assessed by Investigator (Adjuvant Phase Only)

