There remains a significant unmet need for new agents that may increase the survival of patients with CRC undergoing liver metastasectomy. The need is particularly great for the ~95% of patients with mismatch repair proficient (pMMR) metastatic CRC, whose cancers have not responded to pembrolizumab monotherapy [8]. As detailed below, there is evidence of immune-stimulatory effects induced by both 5-FU and oxaliplatin, which we hypothesize will promote tumor response to pembrolizumab.

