1.3.1 Rationale for Perioperative Pembrolizumab-Based Treatment

Identification of new strategies to augment immune-related responses in the broader population of metastatic CRC patients, without dMMR or MSI-H tumors, is essential[31]. Whereas immune checkpoint inhibitors such as pembrolizumab have shown robust single-agent antitumor activity in the ~5% of patients with metastatic CRCs harboring MSI-H or dMMR, novel strategies are needed for the ~95% of patients with MSS or pMMR metastatic CRC [8]. These strategies may include combining pembrolizumab with cytotoxic, targeted, or other immunotherapy agents.

Potentially resectable metastatic CRC represents an ideal clinical setting to assess both the clinical efficacy and immunologic/pharmacodynamics effects of pembrolizumab-based therapies, as the majority of carefully selected patients are ultimately taken to surgery following preoperative therapy (87.3% in the Nordlinger EORTC study)[6]; therefore, a large quantity of tumor tissue is available for immune cell characterization and immune/molecular profiling.

The Primary Objective of this study is to characterize change in the populations of TILs induced by neoadjuvant pembrolizumab-based therapy in patients with metastatic CRC with potentially resectable hepatic metastases. The Primary Endpoint is specifically defined as the proportion of patients with a ≥ 2 -fold increase in the TILs in post- vs. pre-pembrolizumab-based treatment tumor specimens. A ≥ 2 fold increase was the threshold used for 2 prior trials of neoadjuvant immunotherapy [28, 29]. Including a prospective study evaluating the direct immune effects of sipuleucel-T on prostate cancer tissue in the peri-operative setting. Sipuleucel-T, which was FDA-

approved for improved OS in prostate cancer, induced a >2 fold increase in TILs per unit area of tissue [28]. We believe that a doubling in immune infiltration would be deemed as biologic meaningful, whereas magnitudes of change less than that can be more arguable for publication. In two published trials of prostate cancer we have shown that neoadjuvant immunotherapies can induce a >3x increase in TILs[36]. This is in excess of the doubling with which we set the threshold in this trial.

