3.3.2 Exclusion Criteria

The patient must be excluded from participating in the trial if the patient:

1. Is currently participating and receiving study therapy or has participated in a study of an investigational agent and received study therapy or used an investigational device within 4 weeks of the first dose of treatment.

Note: Patients who have entered the follow-up phase of an investigational study may participate as long as it has been 4 weeks since the last dose of the previous investigational agent or device use.

2. Has a diagnosis of immunodeficiency or is receiving chronic systemic steroid therapy (in dosing exceeding 10 mg daily of prednisone equivalent) or any other form of immunosuppressive therapy within 7 days prior to the first dose of trial treatment.
3. Has a known history of human immunodeficiency virus (HIV) infection. No HIV testing is required unless mandated by local health authority.

Phase 2, Pembrolizumab, Vactosertib

4. Has an active autoimmune disease that has required systemic treatment in past 2 years (i.e., with use of disease-modifying agents, corticosteroids, or immunosuppressive drugs). Replacement therapy (e.g., thyroxine, insulin, or physiologic corticosteroid replacement therapy for adrenal or pituitary insufficiency) is not considered a form of systemic treatment and is allowed.
5. Has active Hepatitis B (defined as Hepatitis B surface antigen [HBsAg] reactive) or active Hepatitis C virus (defined as HCV RNA [qualitative] [32] is detected) infection.
6. Has received prior anti-cancer mAb, systemic anticancer therapy other than FOLFOX (including investigational agents), targeted small molecule therapy, or radiation therapy within 14 days prior to the first dose of study treatment (Day 1). Note: patients must have recovered from all AEs due to a previous therapies to ≤Grade 1 or baseline. Patients with Grade 2 neuropathy or alopecia are eligible. If a patient received major surgery, they must have recovered adequately from the toxicity and/or complications from the intervention prior to starting study treatment.
7. Has received FOLFOX less than 7 days prior to the first dose of study treatment (Day 1). Has not recovered (i.e., ≤Grade 1 or at baseline) from AEs due to FOLFOX chemotherapy. Note: Patients with ≤Grade 2 neuropathy or alopecia are exceptions to this criterion and may qualify for the study.

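### The baseline biopsy must post-date only lead-in chemotherapy, so for up to about 13 days other anticancer therapy can follow it and enter the TIL comparison

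*Combined protocol and SAP*

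**What the plan says.** Section 1.3.1 states the primary objective as to "characterize change in the populations of TILs induced by neoadjuvant pembrolizumab-based therapy". The endpoint is the proportion of patients with at least a 2-fold rise in TILs from the pre-treatment to the post-treatment specimen. The trial is single-arm, so the baseline specimen is the only comparator.

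Two eligibility rules fix what can happen around that specimen:

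- Inclusion 7 (Section 3.3.1): "Newly-obtained is defined as a specimen obtained after last dose of standard of care lead-in chemotherapy [if applicable] and within 28 days prior" to the first pembrolizumab dose.
- Exclusion 6 (Section 3.3.2) bars anticancer antibody, systemic therapy other than FOLFOX, "targeted small molecule therapy, or radiation therapy within 14 days prior to the first dose of study treatment (Day 1"). FOLFOX has its own rule in exclusion 7: "Has received FOLFOX less than 7 days prior to the first dose of study treatment (Day 1").

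Section 1.3.3 describes the specimens as "Baseline liver tumor biopsies (just prior to administration of neoadjuvant treatment"), without a day limit. Section 8.4.1 admits to the primary analysis every patient with an evaluable pair, with no condition on treatment given between biopsy and Day 1.

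**The concern.** The order of biopsy and prior therapy is controlled for one kind of therapy only. Lead-in chemotherapy must be finished before the biopsy. Nothing equivalent is said for antibody, targeted therapy or radiation, and their 14-day bar is shorter than the 28-day biopsy window.

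If such therapy falls between the two specimens, its effect on TILs is counted as part of the change after pembrolizumab plus vactosertib. In a single-arm trial no other comparison would reveal it. The protocol itself accepts that background anticancer treatment can act on the immune system: Section 1.1 says "there is evidence of immune-stimulatory effects induced by both 5-FU and oxaliplatin". At stake is the attribution of individual pairs in a test that rests on 17 patients, where one or two reclassified pairs can matter. The effect could go either way: intervening therapy could raise TILs and imitate a response, or lower them and hide one.

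**Working it through.** **Step 1. The rules on one time line (days before C1D1)**

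| Rule | Source | What it controls |
|---|---|---|
| Biopsy allowed from day -28, after lead-in chemotherapy only | Inclusion 7 | Age of specimen; order relative to lead-in chemotherapy |
| Antibody, other systemic, targeted therapy, radiation barred from day -14 | Exclusion 6 | Last permitted day is -15 |
| FOLFOX barred in the last 7 days | Exclusion 7 | As lead-in, it must already precede the biopsy |

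Earliest biopsy is day -28 and latest permitted other therapy is day -15. The gap is 28 - 15 = 13 days.

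**Step 2. What other text closes**

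- Investigational agents: exclusion 1 bars a patient who received one or "used an investigational device within 4 weeks of the first dose of treatment". Four weeks covers the whole 28-day window. (Exclusion 6 also names investigational agents, with 14 days; the two should be reconciled.)
- Prior immunotherapy: barred by exclusion 16.
- Liver-directed therapy to the biopsied lesion: barred for a year by exclusion 9.
- Antibody given with lead-in chemotherapy: under inclusion 2b "the antibody must be omitted from the final cycle of chemotherapy prior to pembrolizumab".
- Any therapy that the treating investigator thinks might confound the results: exclusion 14, at discretion.
- Section 6.5 ties its prohibition to the treatment period. Section 6.5.2 speaks both of restrictions during the study and of use alongside study treatment, so its reach before Day 1 is arguable.

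What remains is mainly radiation to other sites (inclusion 1 allows the primary tumor in place) and stand-alone antibody or targeted therapy. No passage expressly requires the biopsy to follow these.

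**Step 3. The plan's own figure**

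Section 8.2.1 gives 17 pairs, 10% null, 40% alternative, one-sided 0.05, power 0.91. With the arcsine effect size h = 2·asin(√0.4) - 2·asin(√0.1) = 1.369 - 0.644 = 0.726, power = Φ(h√17 - 1.645) = Φ(1.348) = 0.911. The plan's figure is reproduced by this approximation. The plan states no cut-off. The smallest count with exact size at most 0.05 is 5 of 17: size 0.022, power 0.874 (4 of 17 has size 0.083). I use 5 of 17 below.

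**Step 4. Sensitivity to a few affected pairs**

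The documents give neither the number of such pairs nor the effect of such therapy on TILs. Assume no study-drug effect, 2 affected pairs with chance q of a 2-fold rise, and 15 pairs at 10%. For A ~ Binomial(15, 0.10): P(A≥5) = 0.0127, P(A≥4) = 0.0556, P(A≥3) = 0.1841. Then

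P(at least 5 positives) = (1-q)²·P(A≥5) + 2q(1-q)·P(A≥4) + q²·P(A≥3).

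- q = 0.30: 0.49·0.0127 + 0.42·0.0556 + 0.09·0.1841 = 0.046
- q = 0.50: 0.25·0.0127 + 0.50·0.0556 + 0.25·0.1841 = 0.077

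The same calculation for other numbers of affected pairs:

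| Affected pairs of 17 | q = 0.30 | q = 0.50 |
|---|---|---|
| 0 | 0.022 | 0.022 |
| 1 | 0.032 | 0.043 |
| 2 | 0.046 | 0.077 |
| 4 | 0.086 | 0.200 |

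**The case against.** The strongest reply is that this is a corner case. The biopsy is a screening procedure, taken after consent and after CT has re-confirmed resectability. A patient awaiting liver resection would seldom start radiation or a stand-alone agent between that biopsy and C1D1. Most classes of therapy are already barred, and exclusion 14 lets the investigator refuse the rest. This stands as to frequency. It does not close the gap, because exclusion 14 depends on opinion and the analysis population in Section 8.4.1 does not flag such a pair.

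A reader might also infer that the lead-in chemotherapy interval is itself a defect, since the biopsy could be taken the day after chemotherapy and resection could follow on day 42, a difference of 42 - 1 = 41 days. The documents do not support that. Those biopsies already follow chemotherapy, and treating in the post-FOLFOX window is the stated design. The extreme also needs C1D1 on day 42 - 14 = 28 or later, against a planned interval of about 2 weeks. The direction of any drift is unknown: if chemotherapy had already raised TILs at biopsy, a further 2-fold rise would be harder to reach.

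Nor is the phrase in Section 1.3.3 a contradiction. It is background description without a day limit; inclusion 7 sets the operative window.

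**Conclusion.** The gap is real but narrow. A pair can meet every explicit timing criterion with up to about 13 days in which other anticancer therapy followed the baseline biopsy, and its TIL change would then include that therapy's effect in addition to the study drugs'.

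A reader might infer that the measured change reflects earlier treatment rather than pembrolizumab plus vactosertib. Nothing in the documents shows that: only pairs with intervening therapy are touched, and their number may be zero. A reader might likewise apply a higher background rate to everyone. With 15%, 20% or 25% in all 17 patients the chance of at least 5 positives is 0.099, 0.242 or 0.426. Those rates have no source in the documents, and this route would reach only a few patients. They illustrate how much rests on the unexplained 10% null, which is a separate matter.

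The sensitivity range of 0.046 to 0.077 rests on three assumptions: 2 affected pairs, a 30% to 50% chance of a 2-fold rise in them, and the 5-of-17 cut-off. It is not an estimate. The sample size does not depend on this point. The change is worth making because it is cheap and protects the only comparator.

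**What to change.** In inclusion 7, define the baseline specimen as obtained after the last dose of any prior anticancer therapy, not only lead-in chemotherapy, within the existing 28-day window.

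In Section 8.4.2:

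1. List for each pair the days from last anticancer therapy to biopsy and to resection.
2. Show the proportion with at least a 2-fold rise descriptively by lead-in status.
3. If any pair had therapy between biopsy and Day 1, repeat the primary proportion without it.

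Do not make the primary conclusion conditional on the non-lead-in patients. Their number is unknown and may be zero, so such a condition would be an unplanned and unpowered gate.

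The cost is slightly tighter biopsy scheduling. Because exclusion 6 already stops other therapy by day -15, days -14 to -1 stay open for the biopsy. A patient given therapy unexpectedly after the biopsy would no longer meet inclusion 7 on that specimen. Section 6.1.1 already records prior treatments, the interval from FOLFOX or CapeOx to pembrolizumab, and medications within 28 days of Day 1, so the listing needs little new data. For patients already enrolled, the listing and the repeat analysis still apply.
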